General Study Design: The proposed study is a prospective, randomized, clinical trial with attention control under the direction of the dual PIs, a behavioral scientist and a virologist. The study team is also made up of investigators from infectious diseases, mind-body medicine, geriatrics, and biostatistics. Subjects will be randomized to participation in an 8-week group MBSR course as the study intervention or to the Health Enhancement Program (HEP) as the active control arm. The study population will consist of 120 individuals, 50 years old or older, long-term (5 years on ART or longer) HIV-infected adults with well-controlled plasma viremia. Randomization will be stratified to achieve balanced distribution between the groups based on gender and study site. The experimental group will participate in the 8-week MBSR course followed by six, once-per-month booster sessions, and the control group will participate in HEP, a validated group attention control condition for MBSR maintaining subjects inert to mindfulness, with additional monthly educational meetings for

six months. Both groups will be evaluated using two sets of measures: biological markers associated with chronic inflammation (IL-6, CRP, sCD14, d-dimer) and measures of psychosocial stress (anxiety, depression, fatigue, and mindfulness). Subjects will be assessed at three time points: baseline, 8 weeks (immediately after completion of MBSR intervention), and 6-months post MBSR course (immediately after completion of booster sessions). We will use mixed linear and structural equation model to test study hypotheses.

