Intervention: Mindfulness-Based Stress Reduction (MBSR) Course: The MBSR course will follow the approved curriculum by the University of Massachusetts Medical School. Participants will attend 8 weekly sessions, 2.5 hours each, and a 5 hour silent retreat during the 6th week of the program. Two cohorts of MBSR sessions (in concurrence with HEP attentive control sessions) will be conducted in groups of 30 subjects each. Formal mindfulness meditation methods taught in the MBSR course include: Body Scan Meditation (a supine meditation), Gentle Hatha Yoga (practiced with mindful awareness of the body), Sitting Meditation (mindfulness of breath, body, feelings, thoughts, and emotions), and Walking Meditation. Informal Mindfulness Meditation Practices (mindfulness in everyday life) include: 1) awareness of pleasant and unpleasant events, and, 2) deliberate awareness of routine activities and events such as eating, weather, walking, and interpersonal communication. Daily home assignments include a minimum of 30 minutes daily formal mindfulness practices and 5-15 minutes informal practice, 6 days per week for the entire duration of the course. Course sessions will consist of discussions oriented around weekly homework assignments, including an exploration of obstacles, and development of self-regulatory skills and capacities. Monitoring for completion of course assignments and mindfulness practice will also be recorded on a weekly basis using a daily online log. [name] will facilitate the MBSR course. She has taught MBSR to a wide range of patients and health professionals since 2006, and is a Certified MBSR Teacher, the highest level of teacher recognition by the University of Massachusetts Center for Mindfulness. After completion of the 8-week MBSR course, subjects will meet 6 times monthly for a 1-hour refresher session. A monthly online log will be used to record frequency of practice over this 6-month period. Subjects will receive biweekly email reminders to log their practice adherence.

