Potential Challenges, Proactive Measures, Alternative Strategies: Although the HEP active control intervention provides the strongest RCT design, we are aware that it may also pose a challenge in observed outcomes if the effect size of our intervention is small. This is a plausible scenario for two reasons: (1) the attention effect of the active control intervention and (2) elements of the HEP intervention directly reducing psychosocial stress. To account for this possibility, statistical analysis will also include within subject differences. In addition, the sessions of HEP that could most influence stress reduction (i.e., physical activity)^{58,59} will be replaced by educational sessions. Elements such as the weather, and community illnesses associated with weather (i.e., colds, flu, etc.) may impact outcomes of the proposed study. To account for this potential impact, both arms of the study will take place concurrently. Both weekly sessions (one MBSR and another HEP) will take place during the same week in the exact same location (a conference room at Mount Sinai Hospital).

Participants and Recruitment: Subjects will be recruited at the Mount Sinai Health System in Manhattan, New York. In 2013, an integrated health system was created through the merger of Mount Sinai Medical Center and Continuum Health Partners. It is expected that the study will be able to recruit enough subjects at

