The list of eligible patients identified through the electronic medical record will be reviewed with each HIV Primary Care Provider (PCP) and permission requested from them for the RC to contact each of their eligible patients at the next clinic visit. If a PCP indicates not to contact a patient, the reason will be recorded. The patient's participation in this study will play no role in how the PCP manages his or her care. If permission is given, the RC will use a scripted explanation to explain the study to the patient including the inclusion and exclusion criteria. If the patient is interested in participating, he or she will undergo informed consent. The RC will place emphasis on the time demands of the intervention in order to screen out those that are unlikely to adhere to the demands of the intervention. After obtaining Informed Consent, the RC will assign a study identification number, collect demographic and contact information, and a blood sample will be collected to determine baseline IL-6 levels. Each consented subject that meets all inclusion criteria will be invited to join the study and complete three subsequent research visits (separate from the MBSR or HEP sessions). At these visits, the psychological assessments will be completed and blood will be collected. Separate blood draws will also occur within one week of each of these 3 study visits for the second measure of IL-6 values.

Measurement of Biological Markers: Inflammatory biomarkers to be measured belong to one or more of four broad-spectrum categories: i) general (IL-6, CRP), ii) innate immunity (IL-6, CRP, sCD14), iii) microbial translocation (sCD14), and, iv) system wide-associated (CRP, d-dimer). The selection of biological markers for the study is based on three primary considerations: i) markers which have been unequivocally demonstrated to be increased in HIV-infected adults when compared to uninfected counterparts, ii) markers with strong translational medicine correlates connecting basic immunological inflammation with clinical outcomes, and, iii) markers demonstrating scientific reliability with respect to laboratory assay measurements.^{15-17,22,60,61}

The four markers selected using these criteria are:

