Potential Challenges, Proactive Measures, Alternative Strategies The key challenges when measuring the proposed 4 biological markers (IL-6, hsCRP, sCD14 and d-dimer) result from: 1) expertise and quality control of assay execution, 2) diurnal rhythm expression, and, 3) within subject variability.⁸⁸ To account for these potential challenges proactive measures have been established. First, and critically important, has been the establishment of collaboration with Drs. [name] and [name]. The level of expertise, experience and quality control provided by this lab assures reliability on recorded data. All frozen samples will be processed for execution of biological assays at a single run after completion of all collections. This measure controls for any potential variability during assay execution. The potential challenge of diurnal rhythm expression for all of the 4 biological markers will be addressed by strict serum collection in the three hour period between 3 pm and 6 pm. All blood samples for the entirety of the study will be collected in this three-hour time period and processed immediately, followed by immediate storage at a minus 80-degree freezer, assuring preservation of each marker. The concern of within subject variability is a key issue for IL-6 in particular.⁸⁹ For that reason, a critical approach measure has been established: two separate collections of blood for IL-6 measure at each time point, averaging the value for the two. Although it is recognized that this poses an additional level of demand on subjects, as they have to report to the study site twice for each of the three study time points, given the crucial role of IL-6 as the key biological marker, collecting two separate measures at each study time point provides the strongest level of reliability.

Measures of Psychosocial Stress and Mindfulness: Psychosocial measures will be assessed at 3 time points: baseline, after the 8 week course, and after the subsequent 6 month booster sessions.

The Patient Reported Outcomes Measurement Information System (PROMIS) is a system of highly reliable self-report measures, with substantial qualitative and quantitative evidence supporting validity, developed with funding from NIH.^{90,91} Two instruments have been selected from the PROMIS Neuro-QOL Item Bank v1.0 Short Forms: Anxiety and Fatigue (8 validated items each, for a combined instrument of 16 items).

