Aim 1: To assess the effect of MBSR on biomarkers of chronic inflammation in HIV-infected adults with well-controlled plasma viremia. The primary outcome for the analyses of treatment effectiveness will be IL-6 levels. We will use mixed linear models to assess the effect of the intervention on markers of inflammation. The model will include fixed effect terms for treatment group, time, and time-treatment interactions. In secondary analyses, we will similarly assess the effect of the intervention on secondary markers of inflammation (CRP, sCD14, d-dimer) using appropriate adjustments for multiple comparisons. If there are imbalances in patients’ characteristics across groups, statistical adjustment including these factors as covariates will be performed. All analysis will use an intent-to-treat principle. **Power Calculation:** Sample size calculations were based on the following assumptions: 1) mean baseline IL-6 of 2.0 pg/ml (SD:0.5)^{17,98}; 2) stable IL-6 levels in the control arm; 3) clinical significant effect of MBSR will be a net reduction of IL-6 of >0.5 pg/ml.^{98,99} Under these assumptions, a sample size of 100 patients (50 per group) will provide a power >80% using 2-sided test and a 0.05 significance level. One hundred and twenty study participants will be enrolled. Dropout rates reported in the literature for MBSR studies range significantly (range 0 to 48%, mean 10%). In order to lean on a conservative side a higher dropout rate of 15% is estimated for this study. With a 120 enrolled, a 15% dropout rate provides 102 completed participants. It is quite feasible to recruit 120 patients from this estimated eligible sample of 1,800 subjects at the three recruitment sites (requiring participation of ~7% of the eligible sample).

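### The primary IL-6 model makes no pre-specified use of baseline IL-6 as a covariate or common-baseline constraint, so its treatment contrast, though unbiased in this respect, is less precise than the collected data allow

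*Combined protocol and SAP*

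**What the plan says.** In the combined protocol and SAP, section C (Approach), Aim 1 names IL-6 as the primary outcome, to be analysed with a mixed linear model: "The model will include fixed effect terms for treatment group, time, and time-treatment interactions". No baseline IL-6 covariate is listed. The separate treatment-group term lets the arms differ at baseline.

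Other covariates depend on the data. Data Management and Statistical Analysis compares baseline characteristics between arms by t, Wilcoxon or chi-square tests, and Aim 1 then adjusts for characteristics found to be imbalanced. The tests are named, but the variables to be considered and the cut-off are not.

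The relevant data are all collected. General Study Design says "Subjects will be assessed at three time points: baseline, 8 weeks" and then six months after the course. It also says "Randomization will be stratified to achieve balanced distribution between the groups based on gender and study site". Measurement of Biological Markers provides for "two separate collections of blood for IL-6 measure at each time point, averaging the value for the two". However, Participants and Recruitment uses the word baseline for the screening draw as well: "a blood sample will be collected to determine baseline IL-6 levels".

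**The concern.** A randomised trial with a baseline measurement of its primary outcome can use it in two ways. It can subtract it, as an unconstrained three-visit model does in its treatment-by-time term. Or it can condition on it, by a covariate or by constraining the arms to a common baseline mean. Both are unbiased under randomisation. The second has smaller variance for any correlation below 1.

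The imbalance rule is unlikely to supply the adjustment. If the tests were run at 5% (an assumption), baseline IL-6 would be flagged about one time in twenty by chance. Gender and site are balanced by design and would seldom be flagged at all. The final primary model would also depend on the observed baseline data.

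What is at stake is the width of the primary interval, and power if the true effect is smaller than planned. The control-arm section raises that possibility: using an active control, "it may also pose a challenge in observed outcomes if the effect size of our intervention is small". Its response is "To account for this possibility, statistical analysis will also include within subject differences", but change within subjects is not itself the randomised comparison. Baseline adjustment addresses the same worry and keeps that comparison.

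**Working it through.** **Inputs from Aim 1.** IL-6 SD s = 0.5 pg/ml; planned net reduction 0.5 pg/ml with stable controls; two-sided 0.05; 120 enrolled with 15% dropout, so 120 × 0.85 = 102, or n = 51 per arm.

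**Assumed.** rho, the correlation between IL-6 visit means, is not in the documents; 0.3, 0.5 and 0.7 are used. Equal SD at every visit, raw scale (the plan allows a transformation if needed).

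**The plan's own figure.** At 50 per group, difference 0.5 and SD 0.5, a two-sided t-test has 99.86% power. The stated figure of more than 80% is correct as an inequality.

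**Formulas.**
- Listed model (difference in change): variance = 2(1 − rho) × s² × 2/n.
- Baseline adjusted or constrained equal: variance = (1 − rho²) × s² × 2/n.
- Ratio = (1 + rho)/2 = 0.65, 0.75, 0.85, so the interval narrows by 1 − √((1 + rho)/2).

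At rho 0.5: 2 × 0.5 × 0.25 × 2/51 = 0.00980, SE 0.099; and 0.75 × 0.25 × 2/51 = 0.00735, SE 0.086. Half-widths are 1.98 × SE.

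| rho | SE, listed | SE, adjusted | Half-width, listed | Half-width, adjusted | Narrower by |
|---|---|---|---|---|---|
| 0.3 | 0.117 | 0.094 | 0.23 | 0.19 | 19% |
| 0.5 | 0.099 | 0.086 | 0.20 | 0.17 | 13% |
| 0.7 | 0.077 | 0.071 | 0.15 | 0.14 | 8% |

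**Dropout.** With 60 per arm, 9 per arm missing month 6 and compound symmetry, generalised least squares gives month-6 variance ratios of 0.684, 0.776 and 0.867. Taking 1 minus the square root, the interval narrows by 17%, 12% and 7%.

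**Two draws per visit.** If 0.3, 0.5 and 0.7 were single-draw correlations, averaging two draws gives rho = 2r/(1 + r) = 0.46, 0.67 and 0.82, and the variance reduction (complete data) drops to 27%, 17% and 9%.

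**Shared group effect.** The MBSR course "will be conducted in groups of 30 subjects each", with two cohorts per arm. An assumed ICC adds 2 × ICC × s²/2 to both variances: 0.005 at ICC 0.02 and 0.0125 at 0.05. The variance reduction, 35%/25%/15% without a group effect, becomes 26%/17%/8% at ICC 0.02 and 18%/11%/5% at 0.05.

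**Power (noncentral t, df 100 listed, 99 adjusted).**
- At 0.5 pg/ml with no group effect, the lowest value is 98.8% (listed model, rho 0.3).
- At 0.5 pg/ml and rho 0.3 with a group effect, the listed model has about 95% (ICC 0.02) or 86% (ICC 0.05). These keep participant-level degrees of freedom, which is generous with only four groups.
- At 0.25 pg/ml (half the planned effect, chosen for illustration) with no group effect: 56%/71%/90% listed, 75%/82%/94% adjusted. At rho 0.5 with a group effect, 71% to 82% becomes 53% to 61% (ICC 0.02) or 38% to 42% (ICC 0.05).

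**Simulation check.** With three visits, 102 completers and allocation stratified by gender and site, mean estimates were −0.498 to −0.503 for a true −0.5, with and without the extra terms. At rho 0.5 the half-width was 0.193 for the listed model, 0.194 with gender and site main effects alone, 0.170 with equal baseline means, and 0.167 with equal baseline means plus gender and site.

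**The case against.** An unconstrained group-by-time mixed model is valid and conventional, and it already uses baseline as a visit. Aim 1 separately allows covariate adjustment. The loss depends on a correlation the documents do not give, and averaging two draws per visit pushes that correlation up and the loss down. At rho 0.7 the interval narrows by only about 0.01 pg/ml either side, against a planned effect of 0.5. All of this stands. It limits the size of the point, but not its direction: for any rho below 1 the listed contrast is the less precise one.

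A reader might infer more than the documents support:
- **That missing gender and site terms widen the interval.** Time-constant terms cancel from a change contrast with complete data. They help slightly once baseline is adjusted for. The reason to include them is that randomisation is stratified on them.
- **That much larger gains are available.** If only post-baseline visits were modelled, adjustment would cut the variance by rho², up to 49% at rho 0.7. Aim 1 does not state which visits are outcomes, but three assessments including baseline, a time term, and sizing on a net reduction against stable controls all point to a three-visit model. The large figures should not be relied on.

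**Conclusion.** The point holds as a matter of efficiency and pre-specification. It would be wrong to infer that the contrast is biased by these omissions: randomisation protects it, and the simulation agrees. It would also be wrong to infer that the trial is underpowered for its planned effect on this account: on the plan's own inputs with no group effect, power is at least 98.8% with or without adjustment. That reassurance is conditional, since an assumed group ICC of 0.02 to 0.05 brings unadjusted power at rho 0.3 to about 95% to 86%.

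What is lost is 8% to 19% of interval width for rho from 0.7 to 0.3, and less with dropout or a group effect. There is a matching loss of power for the smaller effect that the plan itself regards as plausible. These sizes rest on an assumed rho, SD 0.5 at every visit and the raw scale. The change is worth making because it is free, not because the listed analysis is invalid.

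**What to change.** Pre-specify one primary model in Aim 1, either:

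- (a) post-baseline IL-6 on treatment, visit, treatment-by-visit, baseline IL-6, baseline-by-visit, gender and site; or
- (b) a three-visit model with baseline means constrained equal across arms, plus gender and site.

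Define baseline IL-6 as the mean of the two baseline-visit draws, not the screening draw. Use this fixed set in place of adjustment triggered by baseline tests. Label any further covariate adjustment, and the within-subject differences, as supportive.

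The cost is analysis-plan wording only. Baseline IL-6, gender and site are already collected, and the sample size is unchanged.

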The Beck Depression Inventory (BDI-II)⁹² is a reliable and valid self-report measure of depression.⁹³ The

Total Score of the BDI-II will be used to measure depression. This 21-item measure asks about how the subject has been feeling in the “past two weeks including today” and requires 5-10 minutes to complete.

The Five Facet Mindfulness Questionnaire (FFMQ) will be used in the study to measure mindfulness. This is a validated scale is commonly used in MBSR scientific studies. FFMQ will also provide an indication of rates of adoption of MBSR activities by participants, and permit analysis within 5 separate subscales: observing, describing, acting with awareness, nonjudging of inner experience, and nonreactivity of inner experience.⁹⁴⁻⁹⁷

We will also evaluate the feasibility and acceptability of each intervention condition. Attendance records will provide completion and retention rates. In addition, the RC will conduct a structured interview with each subject at the visit following the 8 week course to assess acceptability of the intervention.

Data Management and Statistical Analysis: We will use SPSS version 22 (IBM), and TrueCrypt 7.1a software (TrueCrypt Foundation) to enter, manage, and encrypt all electronic data. We will perform random checks and double entry of data to minimize coding errors. Data will be stored in a secured network that is backed up daily by Mount Sinai’s Information Technology Department. The distributional properties of study outcomes will be evaluated and appropriate transformations will be applied, if necessary. The equivalence of baseline characteristics of study groups will be assessed with the t-test, Wilcoxon test, or chi-square test, as appropriate. We will also assess patterns of missing data and use multiple imputation or full information maximum likelihood methods, if missing at random.

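### On the ordinary reading of Aim 1, adding an imbalanced baseline factor as a covariate leaves the time-by-treatment contrast essentially unadjusted, and the choice of covariates depends on observed imbalance

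*Combined protocol and SAP*

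**What the plan says.** The analysis text is in C. Approach, under Data Management and Statistical Analysis and under Aim 1.

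- Outcome: "The primary outcome for the analyses of treatment effectiveness will be IL-6 levels".
- Model: "The model will include fixed effect terms for treatment group, time, and time-treatment interactions". No other interaction is mentioned, and the contrast that tests MBSR is not named.
- Visits (General Study Design): "Subjects will be assessed at three time points: baseline, 8 weeks (immediately after completion of MBSR intervention), and 6-months post MBSR course".
- Target effect (Aim 1, power calculation): a net IL-6 reduction of more than 0.5 pg/ml against a stable control arm.
- Adjustment (Aim 1): "If there are imbalances in patients’ characteristics across groups", then "statistical adjustment including these factors as covariates will be performed". There is no threshold, no list of factors, and no statement on whether a covariate interacts with time.
- Baseline check (Data Management and Statistical Analysis): "The equivalence of baseline characteristics of study groups will be assessed with the t-test, Wilcoxon test, or chi-square test, as appropriate". No margin is given.
- Stratification (General Study Design): "Randomization will be stratified to achieve balanced distribution between the groups based on gender and study site". Neither factor is listed in the model.

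**The concern.** Baseline is one of the three assessments and the target is a net reduction, so the natural test is a difference between arms in change from baseline. A patient factor that is constant over time, entered as a main effect, shifts a patient's values equally at every visit and so drops out of change. If such a factor predicts how IL-6 changes and is imbalanced by chance, the report would call the result adjusted while the primary estimate still carried the imbalance.

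The rule that selects covariates is also weak. A non-significant t, Wilcoxon or chi-square test does not show that the arms are alike, and a significant one does not show that the factor matters for IL-6 change. Either way, the covariates are settled only after the data have been seen.

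**Working it through.** **1. The plan's own figures.** With 50 per group, difference 0.5 and SD 0.5, the standard error is 0.5 × √(2/50) = 0.1, so z = 5 and power is about 0.999. The stated power of over 80% holds. Also 120 × 0.85 = 102. This point affects neither figure.

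**2. Algebra, complete data, visit as a category.** Let the mean for patient i in arm g at visit t be μ(g,t) + βx(i), where x does not vary over time. The fitted value is μ̂(g,t) = ȳ(g,t) − β̂x̄(g). The contrast is [μ̂(1,t) − μ̂(1,0)] − [μ̂(0,t) − μ̂(0,0)]. Each β̂x̄(g) appears once with a plus and once with a minus, so the contrast equals the unadjusted one. If the slope may differ by visit, a term −(β̂(t) − β̂(0)) × (x̄(1) − x̄(0)) remains. That term is the correction wanted.

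**3. Numerical check.** The simulations had three visits, 60 per arm, a random-intercept model and no true effect. Assumed values were a random-intercept and residual SD of 0.35 each, an imbalance of 0.35 SD, and a factor that shifts IL-6 change by 0.15 pg/ml per SD. The expected bias is 0.35 × 0.15 = 0.0525 pg/ml.

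| 6-month contrast (pg/ml) | No covariate | Main effect | Factor × visit |
|---|---|---|---|
| One complete data set | −0.00935 | −0.00935 | −0.0314 |
| 15% random dropout, mean of 200 trials | +0.059 | +0.059 | +0.006 |
| 15% dropout depending on the factor, mean of 200 | +0.058 | +0.059 | +0.004 |
| Factor affects level only, 15% random dropout, mean of 200 | +0.0065 | +0.0067 | +0.0061 |

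In row 1 the first two models agree to eight decimals (SE 0.0896). In row 2 the factor-by-visit terms remove 0.059 − 0.006 = 0.053, which matches the expected 0.0525. The remaining 0.006 is about the simulation error, 0.09/√200 ≈ 0.006. With dropout the main effect moves single-trial estimates a little (on average about 0.008, at most 0.034), but not towards the truth. Row 4 shows that a factor related only to IL-6 level leaves nothing to correct.

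**4. The baseline tests.** At 60 per arm, an observed difference must reach 1.96 × √(2/60) = 0.358 SD to give p<0.05. Power to flag a true shift is about 19% at 0.2 SD, 38% at 0.3 SD and 78% at 0.5 SD. With 10 independent characteristics, the chance that at least one is flagged is 1 − 0.95^10 = 40%, whether or not that one predicts change.

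**5. Error rates.** In step 3 the factor's correlation with change is 0.15/√(0.15² + 2 × 0.35²) = 0.29. Over 20,000 randomized null trials, type I error was 4.9% unadjusted and 5.0% with the factor adjusted for in the change comparison. In the 4.7% of trials with an observed imbalance of at least 0.36 SD, it was 8.8% and 4.1%.

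For a general correlation r, given the factor's statistic z, the change statistic is approximately normal with mean rz and variance 1 − r². Averaging over |z| > 1.96 gives:

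| Assumed r | 0.3 | 0.4 | 0.5 |
|---|---|---|---|
| Conditional type I error, integration | 9.8% | 13.5% | 18.5% |
| Same, simulated at 51 per arm | 10.5% | 13.7% | 19.4% |
| Residual SD ratio after adjustment, √(1 − r²) | 0.95 | 0.92 | 0.87 |

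With factor-by-visit terms, the simulated conditional rates were 4.3% to 5.8%. The last row is the precision forgone when the factor is left out of the change comparison.

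**The case against.** The strongest reply is that the plan does not commit to the reading that makes the adjustment inert. It names no test contrast, does not say whether baseline IL-6 is an outcome row or a covariate, and does not exclude covariate-by-time terms. The power inputs use the SD of IL-6 level, and the discussion of the HEP control says within-subject differences will also be analysed, which suggests they need not be the sole analysis. In the complete data set above, covariate adjustment does move other estimates: the treatment main effect goes from 0.031 to −0.065, and the 6-month difference from a post-baseline model goes from 0.017 to −0.069 once baseline IL-6 and the factor are added. This objection stands in part, and the conclusion is therefore tied to the ordinary reading. That reading is still the best supported, because the plan writes out its interactions and lists none with covariates, and the target is a net reduction from a measured baseline.

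It is also fair to say that Aim 1 does not refer to the baseline tests or to any p-value. The link is inferred, although no other check of balance is described.

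A reader might infer three stronger things that the documents do not support:

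- That the adjustment can never alter the estimate. Exact invariance needs complete data, and the plan expects 15% dropout.
- That every imbalance goes uncorrected. Factors that affect level alone already cancel.
- That the trial's false-positive rate is 9% to 19%. Those rates apply only in trials where a change-predicting factor is imbalanced at p<0.05. Over all randomizations the rate is about 5%, so the primary test remains valid. The 40% chance of a flag concerns any characteristic, not one that predicts change.

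**Conclusion.** The point holds in limited form. If baseline is an outcome visit, MBSR is tested by time-by-treatment, and covariates are main effects, the stated adjustment leaves the primary contrast unchanged with complete data and removes essentially none of the bias at 15% dropout. The cancellation is algebraic and needs no assumed values. The sizes do: the documents give no correlation between any baseline factor and IL-6 change, so the range 0.3 to 0.5, the 0.35 SD imbalance and the slope of 0.15 are assumptions.

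The cost is conditional bias, some lost precision, and a result described as adjusted when its main contrast is not. The selection rule adds to this, because the covariates are not fixed in advance and difference tests cannot establish equivalence. This is a worthwhile and cheap correction, not a threat to the validity of the primary test or to the stated power.

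**What to change.** In Aim 1, name the time-by-treatment contrast that tests MBSR, including which follow-up visit or visits it uses. Replace the imbalance sentence with wording such as:

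> A short list of prognostic baseline factors, including the stratification factors gender and site, is fixed before the single-run assay of study samples and enters the model with factor-by-visit interactions, whatever the baseline comparisons show.

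The section on biological markers plans to assay all frozen samples in one run after collection ends. That gives a natural deadline, although IL-6 is measured earlier at screening for eligibility.

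Report baseline characteristics descriptively. Label any adjustment for an observed imbalance as a sensitivity analysis, also with factor-by-visit terms.

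The cost is SAP wording and a few degrees of freedom. With three visits, a binary or continuous factor takes 1 + 2 = 3 parameters and the three-site factor takes 2 + 4 = 6, so gender and site together use 9, against 102 × 3 = 306 observations from completers. No new data are needed.
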